5.3. Interim Analyses

This study was designed with a group sequential design to provide an interim analysis for futility. This futility evaluation was removed from consideration prior to its' scheduled occurrence and did not take place.

5.4. Subject Disposition

A tabulation of subject disposition will be tabulated, including the number screened, the number dosed with each treatment, the number in each subject population for analysis, the number that withdrew prior to completing the study, and reasons for withdrawal. The number in each risk group (PS=0 or 1 versus PS=2) will be tabulated.

A by-subject listing of study completion information, including the reason for premature study withdrawal, if applicable, will be presented.

5.5. Demographic and Baseline Characteristics

Baseline, demographic and medical history information will be summarized using descriptive statistics. No formal statistical comparisons will be performed.

Demographic and baseline data will be provided in data listings.

5.6. Efficacy Evaluation

All efficacy analyses will be performed on the ITT population. Analyses on the primary efficacy endpoint will be repeated on the PP population.

Primary Endpoint Definition and Analysis

The primary endpoint, OS, will be defined as the time elapsed between date of randomization and date of death (or censoring) from any cause. Any patient not known to have died at the time of analysis will be censored based on the last recorded date on which the patient was known to be alive.

The primary objective of the trial is to estimate whether GRASPA plus LDAC is more promising than LDAC alone with respect to OS in subjects from 65 to 85 years old with newly diagnosed AML unfit for intensive chemotherapy.

Overall survival will be summarized by treatment group for the ITT population. Summaries will include the number of patients who died during the study, the number of patients who didn't die during the study (censored) with the date of censoring equal to the date that the patient was last known to be alive. Median time-to-event will be estimated from a Kaplan-Meier analysis, with associated survival curves produced. The p-value for this analysis will be provided from the stratified log-rank test, with stratification variable of type of ECOG performance status (0 or 1 versus 2) and will compare the overall survival curves between the two treatment groups. In addition, the hazard ratio and its associated 95% CI will be estimated from a stratified Cox proportional hazards model using the same strata as the Kaplan-Meier analysis (ECOG status) and censoring rules. Forest plots for the OS hazard ratios for the subgroups detailed in Section 4.2.6 will also be produced.

OS event rates at Months 12 and 24 will be summarized by treatment group for the ITT population. Summaries will include the event rate for each treatment group from the Kaplan-Meier analysis, using the estimated proportions at Month 12 and 24. A 95% CI for the difference in event rates between the treatment groups will also be provided.

5.6.1. Sensitivity Analyses for the Primary Endpoint

The analyses described in Section 4.6 will also be repeated on the PP population and separately for patients recruited before and after the protocol amendment to assess sensitivity of results to protocol compliance and amendment.

A further sensitivity analysis will be undertaken based on a stratified Cox Model, stratified for PS (0 or 1 versus 2), and including age (< 70 / ≥ 70) and Karyotype (Intermediate risk / High risk) as covariates.

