Older patients with multiple poor-risk factors have a poorer prognosis and treatment outcome. In a retrospective analysis of 998 old patients treated with intensive induction at the M. D. Anderson Cancer Center, multivariate analysis identified age over 75 years, unfavorable karyotype, poor performance status, creatinine > 1.3 mg/dL, duration of antecedent hematologic disorders > 6 months, and treatment outside a laminar airflow room as adverse prognostic factors. Patients with 3 or more of these factors had expected complete remission rate of less than 20%, 8-week mortality > 50% and one year survival < 10% (Kantarjian, 2006).

Efforts have been made to develop efficacious regimens that are tolerable for older patients. The prototype for low-intensity induction over the last several decades has been low-dose cytarabine, which resulted in complete remission rate of 18% and improved overall survival when randomized to supportive care and hydroxyurea (Burnett, 2007).

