15.3.1 Primary endpoint analysis

The primary endpoint will be analyzed based on the ITT population. Efficacy data will also be analyzed on the Per-Protocol population to assess sensitivity of results to protocol compliance.

The primary objective of the trial is to estimate whether GRASPA plus low-dose cytarabine is more promising than low-dose cytarabine alone with respect to OS in subjects 65-85 years old with newly diagnosed AML unfit for intensive chemotherapy. OS will be calculated from date of randomization to date of death (or censoring).

OS will be summarized using Kaplan-Meier methods. The analysis of OS, will be performed using a stratified log-rank test (stratification factor PS (0, 1 vs 2) to compare treatment groups).

Hypothesis testing will be based on the following relations:

H0 : $\theta = -\log(\lambda) = 0$ and the alternative hypothesis will be H1 : $\theta = \theta 1 > 0$ where λ is the hazard ratio (HR) between the GRASPA plus low-dose cytarabine and the low-dose cytarabine alone groups. In our case (assumption for the median survival times of 2 months and 3.5 months for low-dose cytarabine alone and GRASPA plus low-dose cytarabine respectively) this will mean that H1 : $\theta = -\log(0.5714) = 0.5597$.

A secondary analysis will be performed using Cox's proportional hazards regression model, allowing for the effect of treatment and prognostic factors (ECOG, age and cytogenetic group). For the main criterion of efficacy the significance level will be 0.05 using a two-sided test.

The primary analysis for OS will take place once all patients have completed 12 months in the study. It should be noted however that the study is not powered explicitly for OS and statistical significance in favor of GRASPA plus low-dose cytarabine is not anticipated. A decision as to whether GRASPA appears to be a promising drug in this indication will be based on the numerical values for the hazard ratio for OS. A hazard ratio of ≤ 0.80 will indicate a 20% numerical reduction in the death rate on average over time in the GRASPA group compared to control.

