2.1.1. Primary objective

The primary objective is to evaluate Overall Survival (OS) in AML patients 65 to 85 years unfit for intensive chemotherapy, when treated with GRASPA plus low-dose cytarabine (LDAC) compared to low-dose cytarabine alone (LDAC).

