5.2.4. Adjustments for Covariates

No formal statistical analysis that adjusts for possible covariate effects is planned.

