5.2.6. Subpopulations

Analyses (estimated treatment effects and 95% confidence intervals) will be undertaken in relation to OS, PFS and objective response according to the following subgroups and presented in Forest Plots:

- Gender (male/female)
- ECOG PS (0 versus 1 versus 2)
- Age (< 70 / ≥ 70)
- Karyotype (Intermediate risk / High risk)
- Baseline bone marrow blasts, % (< 20% / ≥ 20% to ≤ 30% / > 30%)
- LDH levels at baseline (normal/elevated/unknown)

- FAB (French-American-British) Classification of AML (M1/2 vs. M4/5 vs. M0/6/7)

Other subgroups may be investigated in exploratory analyses.

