5.6.2.2. Progression-Free Survival (PFS)

PFS was originally defined as death due to progression in the protocol. However, to be consistent with regulatory guidance, which considers death from any cause in its definition, this endpoint was modified to be time elapsed between randomization and disease progression or death from any cause. Patients not known to have any of these events will be censored on the date they were last known to be event-free.

Progressive disease (PD) will be defined according to the section “AML-DISEASE EVALUATION” in the e-CRF as any of the following

- At least a 25% increase of BMBC compared with baseline (defined in the section “AML history / BM evaluation at baseline”, Bone Marrow Aspirate - Analyte - Blast)
- At least a 50% increase of PBBC compared with baseline
- Presence of extramedullary disease

Potential PD events presented by the patients will be reviewed and approved before database lock.

The methods for the analysis of PFS will be the same as those for OS. Specifically, PFS will be analyzed at the time of final analysis using a stratified log-rank test (stratified by PS) and displayed using Kaplan-Meier curves. Furthermore, a Cox model will also be used to test the effect of treatment and will include terms for prognostic factors (PS, age and karyotypic group).

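### The adjusted OS Cox model in SAP 5.6.1 splits age at 70 in a 65-85 population and has no karyotype level for patients without a result

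*SAP*

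**What the plan says.** SAP 2.1.1 describes the population as "AML patients 65 to 85 years unfit for intensive chemotherapy". The primary OS analysis (SAP 5.6) is a log-rank test and a Cox hazard ratio, both stratified by performance status (PS) alone. SAP 5.6.1 adds a PS-stratified Cox model "including age (< 70 / ≥ 70) and Karyotype (Intermediate risk / High risk) as covariates". Protocol 15.3.1 describes the corresponding secondary model as allowing for "prognostic factors (ECOG, age and cytogenetic group", with no age cut and no list of cytogenetic levels.

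For PFS, SAP 5.6.2.2 states that "The methods for the analysis of PFS will be the same as those for OS" and that a Cox model "will include terms for prognostic factors (PS, age and karyotypic group". The coding is not given. SAP 5.6.2.3 names the same factors for RFS, again without coding. The SAP response model (5.6.2.1) contains only treatment and PS.

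The subgroup list in SAP 5.2.6 gives karyotype the same two levels, but it lists "LDH levels at baseline (normal/elevated/unknown". SAP 5.2.8 says that missing data points are in general not substituted. The missing-data category in SAP 5.2.1 applies to summary tables. SAP 5.2.4 says "No formal statistical analysis that adjusts for possible covariate effects is planned".

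**The concern.** The SAP narrows what the protocol wrote. It turns age into a two-level factor and gives no reason for 70. The model then treats patients of 70 and 85 as equivalent, and any age imbalance within that band goes unadjusted. The only adverse age threshold inside 65-85 that the protocol mentions is in section 3.1, where "multivariate analysis identified age over 75 years, unfavorable karyotype, poor performance status" and other factors as adverse.

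The two karyotype levels leave no place for a failed or missing test. Protocol 7.2 excludes APL and CBF-AML, which explains why there is no favourable level, but not what happens to a patient without a result. The model's output table (14.2.1.1.3.1 in SAP 8.1) is labelled ITT, and a complete-case fit would not be ITT if any karyotype were missing.

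Randomisation and the primary analysis balance or adjust for PS only. The 5.6.1 model is the one planned OS analysis that adjusts for age or karyotype, so its coding should not lose information that the trial already holds.

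**Working it through.** **Figure in the plan.** The documents give no figure for age information or missing karyotype. The only design figure nearby is 117 PFS events for 80% power (SAP 5.1). With hazard ratio 2/3.5 = 0.571, 1:2 allocation and two-sided 5%, Schoenfeld's formula gives 81.4% power at 117 events and needs 113 events for 80%. That is close to the plan, and nothing below depends on it.

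**Age: inputs.** Range 65-85 (SAP 2.1.1), cut at 70 (SAP 5.6.1). The age distribution is not in the documents, so it is assumed and varied.

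**Age: formula.** If the log hazard is linear in age, the share of age information kept by a split is the squared correlation R² between age and the indicator age ≥ 70. For ages uniform over a range of length L, with a share p below the cut:

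- covariance = L·p(1−p)/2, variance of age = L²/12, variance of the indicator = p(1−p)
- R² = 3p(1−p)
- p = (70−65)/20 = 0.25, so R² = 3 × 0.25 × 0.75 = 0.5625

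| Assumed ages | Share under 70 | R² kept |
|---|---|---|
| Uniform 65-85 | 25% | 0.56 |
| Truncated normal, mean 74, SD 5 | about 18% | 0.46 |
| Truncated normal, mean 75, SD 5 | 14% | 0.41 |
| Truncated normal, mean 76, SD 5 | 11% | 0.36 |

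The means and SDs are those of the normal distribution before truncation. Over wider assumptions (means 68-78, SD 4-6, or exponentially declining ages), R² runs from about 0.68 for the youngest samples to about 0.14 for the oldest. At least about a third of the linear age information is lost in every case tried. Continuous age keeps all of it.

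**Karyotype: inputs.** 123 patients (SAP 5.1), and no substitution in general (SAP 5.2.8). The share q without a karyotype is not stated. Complete-case fitting drops 123·q patients. If deaths fall in proportion, the SE of the log hazard ratio rises by 1/√(1−q).

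| Assumed q | Dropped | Left in model | SE factor |
|---|---|---|---|
| 0% | 0 | 123 | 1.00 |
| 5% | 6 | 117 | 1.03 |
| 10% | 12 | 111 | 1.05 |
| 20% | 25 | 98 | 1.12 |

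**What this does to the treatment estimate.** With 41 and 82 patients and an age SD of 5 (assumed), the SE of the difference in mean age is 5 × √(1/41 + 1/82) = 0.96 year. With R² = 0.41, the part that the split leaves unadjusted is about 0.96 × √(1 − 0.41) = 0.73 year. If each year multiplies the hazard by 1.02-1.05 (assumed), a typical chance imbalance moves the adjusted hazard ratio by about 1.5-4%. For comparison, with 123 deaths at 1:2 the SE of the log hazard ratio is 1/√(123 × 2/9) = 0.19, so an observed 0.80 has a 95% interval of about 0.55-1.16.

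**Wording conflict.** SAP 5.2.4 rules out covariate-adjusted analyses. SAP 5.6.1, 5.6.2.2 and 5.6.2.3 each plan a Cox model with age and karyotype terms.

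**The case against.** The strongest reply is that little turns on this. Neither the primary test nor the PS-stratified hazard ratio read against 0.80 comes from this model, and sampling error is far larger than the shift from coarse age coding. Using prespecified subgroup categories as covariates is common practice, and continuous age is more efficient only if its effect is roughly linear, which the documents do not establish. All of this stands and limits the weight of the point. It does not give a reason to prefer the split.

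A reader might infer more than the documents support:

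- *That ITT patients will be dropped.* This happens only if some karyotypes are missing. Cytogenetic analysis is an inclusion-visit item (Protocol 8.10) and CBF-AML is excluded on cytogenetic grounds, so most patients should have a result. At 0% missing, nobody leaves.
- *That every adjusted model uses the 70 cut.* It is written only for the OS sensitivity model and the subgroups. It is implied for PFS and unstated for RFS, and the SAP response model has no age term.
- *That this model is the only safeguard against imbalance, or that imbalance is the main threat to the result.* Baseline tables (SAP 5.5) and forest plots by age and karyotype (SAP 5.2.6) are also planned, although they do not adjust.
- *That the right cut is 75.* Protocol 3.1 reports patients given intensive induction, a different population, and it too splits age in two.

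On SAP 5.2.4, the word formal could be read as leaving room for a sensitivity analysis. That reading is hard to square with SAP 5.6.2.2, where the Cox model is to test the treatment effect.

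**Conclusion.** The point holds as a matter of efficiency and completeness in a sensitivity analysis. The age split discards about 44% of the linear age information if ages are uniform and 54-64% under the central normal assumptions. The range over everything tried is about 32-86%. These figures rest on assumed age distributions and a roughly linear effect on the log hazard. The loss of patients is conditional on a missing-karyotype rate that the documents do not give. Even at 10% missing its cost is small: power for an OS hazard ratio of 0.80, if all 123 patients died, goes from 21% to 20%. The decision rule at 0.80 is untouched. The conflict between SAP 5.2.4 and the planned Cox models needs no assumption. The change is worth making because it costs almost nothing and improves the only planned OS model that adjusts for age or karyotype.

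**What to change.** Before database lock, amend the SAP as follows:

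- In 5.6.1, enter age as continuous, either linear or as a prespecified spline.
- In the same model, add an unknown/not evaluable level to karyotype.
- State the same coding for the PFS and RFS Cox models. The added level keeps all ITT patients in the OS and PFS models; RFS is limited to patients who reached CR or CRi in any case.
- Report the number of patients and events in each fitted model.
- Keep the 70 cut for the forest plots only.
- Replace 5.2.4 with a sentence listing the adjusted analyses that are planned.

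The response model needs no age change unless the prognostic-factor logistic model of Protocol 15.3.3 is restored.

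The cost is SAP wording and minor programming. Date of birth and baseline cytogenetics are already collected (Protocol 8.10). Sample size, primary test and primary hazard ratio stay as they are. Label: free improvement.

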5.6.2. Secondary Endpoint Definitions and Analyses

Secondary endpoints will be assessed on both the ITT and PP populations.

5.6.2.1. Complete Remission (CR), Complete Remission with Incomplete Recovery (neutrophil or platelet recovery, CRi, CRp), Partial Remission (PR)

Definitions for CR, CRi, and PR can be found in Table 4 below. This information will be collected in the section “AML-disease evaluation.” Responses are entered by the site in accordance with various criteria. Exploratory analyses may include imputed responses (not site defined) based on the data available per the criteria in Table 4 for the derivation of response.

Table 4: Definitions of CR, CRi, PR, Relapse

Category	Definition according to protocol V4 to V6	Definition according to protocol V7
Morphologic leukemia-free state	Bone marrow blasts < 5% No extramedullary disease	
Complete remission (CR)	Morphologic CR Bone marrow blasts < 5%; absence of blasts with Auer rods; absence of extramedullary disease; absolute neutrophil count $> 1.0 \times 10^9/L$ (1000/ μ L); platelet count $> 100 \times 10^9/L$ (100 000/ μ L); patient independent of transfusions Cytogenetic CR Cytogenetic normal (in those with previously abnormal cytogenetics) Molecular CR Molecular studies negative	
CR with incomplete recovery (CRi)	All CR criteria except for residual neutropenia ($< 1.0 \times 10^9/L$ [1000/ μ L]) OR thrombocytopenia ($< 100 \times 10^9/L$ [100 000/ μ L]). patient independent of transfusions	
Partial remission (PR)	All hematologic criteria of CR; decrease of bone marrow blast percentage to 5% to 25% And normalization of blood counts	
Relapse following CR	Bone marrow blasts $\geq 5%$; OR reappearance of blasts in the blood OR Development of extramedullary disease	

Percentages of patients with CR, CR or Cri, and PR will be calculated and presented by treatment group. All other subjects will be considered non-responders for determining the denominator. This objective response rate data (i.e. CR, CRi or PR) will be analyzed based on a logistic regression model with both treatment and PS included in the model. The treatment effect will be summarized with an adjusted Odds Ratio (OR) and 95% confidence interval. Percentage of patients with objective response will be calculated and associated exact 95% CIs will be presented by treatment group.

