4.3.2 Secondary endpoints

- Percentage of patients with Complete remission (CR), Complete remission with incomplete recovery (neutrophil or platelet regeneration, CRi), Partial remission (PR)
- Progression-free survival (PFS) defined as the time elapsed between randomization and resistant disease or relapse or death from any cause
- Relapse Free Survival defined only for patients who achieved CR or CRi as the time elapsed between date of CR/CRi and date of disease relapse or death from any cause
- Percentage of patients who need transfusions (red blood cells and/or platelets), number of transfusions by patient
- Patient quality of life evaluated using the EORTC QLQ-C30 version 3 scale
- Number of hospitalizations (except scheduled protocol visit) required during the study
- Safety of GRASPA in combination with low-dose cytarabine, with specific attention to :
 - o Grade 3 or 4 of Pancreatic toxicity
 - o Grade 3 or 4 of hepatic toxicity, allergic reaction or coagulation event
 - o Grade 3 or 4 of hypoproteinemia or hyperglycemia/diabetes
 - All other non-hematologic Grade 4 toxicities

(*NB* grading reference used: NCI CTCAE version 4.0)

- Pharmacokinetic and pharmacodynamic parameters:
 - o Plasma concentrations of asparagine, aspartate, glutamine, glutamate
 - Whole Blood L-asparaginase activity
- Immunogenicity by measuring titer of anti-L-asparaginase antibodies
- Biomarker cytogenetic testing (optional)
- Measurement of the following parameters on harvested bone marrow tumor cells (optional):
 - Asparagine synthetase protein expression
 - Asparagine synthetase mRNA expression
 - In vitro sensitivity to L-asparaginase

(See also section 8.8 for details)

Table 3 hereafter provides the definitions of response criteria in AML.

Category	Definition
Complete remission (CR)*	Bone marrow blasts < 5%; absence of blasts with Auer rods; absence of extramedullary disease; absolute neutrophil count > $1.0 \times 10^{9}/L$ (1000/µL); platelet count > $100 \times 10^{9}/L$ (100 000/µL); red blood cell transfusion independence
CR with incomplete recovery (CRi)	All CR criteria except for residual neutropenia ($< 1.0 \times 10^{9}/L [1000/\mu L]$) or thrombocytopenia ($< 100 \times 10^{9}/L [100 000/\mu L]$)
Partial remission (PR)	all hematologic criteria of CR; decrease of bone marrow blast percentage to 5% to 25%; and decrease of pre-treatment bone marrow blast percentage by at least 50%

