6.1 Type of trial

This is a multicenter, open label, randomized, controlled phase IIb trial.

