15.3.3 Secondary endpoint analysis

Efficacy endpoints

All efficacy secondary endpoints will be analyzed in the ITT and PP populations.

Progression-free survival (PFS) will be analyzed as a secondary criterion of efficacy. PFS will be defined as the time from date of randomization and resistant disease or relapse or death from any cause. Any patient not known to have died at the time of analysis will be censored based on the last recorded date on which the patient was known to be alive (i.e. their status must be known at the censored date and should not be lost to follow up or unknown). PFS will be analyzed at the time of final analysis using a stratified log-rank test (stratification factor, PS). A Cox model will also be used to test the effect of treatment and will include terms for prognostic factors (PS, age and cytogenetic group).

The analysis of objective response rate (i.e. CR or PR) will be performed using logistic regression including treatment factor and PS. Secondary analysis will be performed where the logistic regression model will allow for the effect of treatment, and will also include prognostic factors as for OS and PFS. Percentage of patients with CR, CRi, CRp and PR will be calculated and associated exact 95% CIs will be presented by treatment group. Median duration of response from onset of response (RFS) will be calculated and summarized by treatment group for the subset of responders.

Absolute and relative change from baseline EORTC quality of life (QoL) questionnaire scores will be described in each treatment group. EORTC QoL questionnaire scores will be compared across time in each treatment group using a mixed model for repeated data.

Time until QoL deterioration will be defined as a decrease in QoL score from baseline without any return to a better state during the study. A threshold of 10% decrease in QoL score will be primarily used. Other thresholds may be used as exploratory analyses. Death will also be considered as a QoL deterioration. Time to QoL deterioration will be summarized using Kaplan-Meier methods and will be compared between treatment groups using a stratified log-rank test (stratification factor, PS).

Percentage of patients who need transfusions (red blood cells and/or platelets), mean number of transfusions by patient and mean number of hospitalizations (more than over 24 hours) required during the study will be described with their corresponding 95% CI in each treatment group.

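### The main response analysis pools site-entered calls across protocol versions with no rule on which criteria govern, and its composite differs from the protocol's without being declared

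*SAP*

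**What the plan says.** Protocol 6.1 sets the design: "This is a multicenter, open label, randomized, controlled phase IIb trial". Neither document describes a masked or central review of response. The one trace is the title of SAP listing 16.2.6.2, which mentions central readings but has no procedure behind it.

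On the source of the response data, SAP 5.6.2.1 states: "Responses are entered by the site in accordance with various criteria". On a derived response it states only: "Exploratory analyses may include imputed responses (not site defined) based on the data available per the criteria in Table 4". Table 4 is headed with two sets of definitions, one for protocol V4 to V6 and one for V7. The change history (protocol Appendix 11) confirms that V7 re-defined response.

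On the composite, the SAP reads "This objective response rate data (i.e. CR, CRi or PR) will be analyzed based on a logistic regression model", with treatment and performance status in the model. Protocol 15.3.3 reads "The analysis of objective response rate (i.e. CR or PR) will be performed using logistic regression including treatment factor and PS". The SAP also plans separate percentages for CR, for CR or CRi, and for PR. SAP section 6, which lists changes to the planned analyses, covers the PFS definition, the move to OS and the dropped interim analysis. It does not mention response.

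**The concern.** Three things leave the response result less well defined than it should be.

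- **Who decides.** Sites know the arm, and their category goes directly into the main analysis. SAP 5.6.2.2 has potential progression events reviewed and approved before database lock; response has no equivalent step.
- **Which criteria.** Patients assessed under V4 to V6 and under V7 enter one regression with no governing definition. The before-and-after-amendment split in SAP 5.6.1 covers only the primary endpoint.
- **Which composite.** Under the protocol's parenthesis, a patient with marrow blasts below 5% but low platelets is a failure, while one with up to 25% blasts and recovered counts can be a success. The SAP reverses this for CRi without saying so, although SAP section 2 undertakes to set out differences from the protocol. Both documents also name CRp, and neither defines it.

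Response is tested at the two-sided 0.05 level (SAP 5.2.1) and has its own subgroup forest plots (SAP 5.2.6). It is also one of the endpoints the SAP Introduction weighs together when judging activity. Relapse-free survival starts at CR or CRi, so it inherits whatever definition was used.

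**Working it through.** The documents give no expected response rate, power or sample size for objective response, so there is no planned figure to reproduce. The check sets the texts side by side and then shows scale under stated assumptions.

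**Texts compared**

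| Item | Protocol V7 | SAP |
|---|---|---|
| Composite | CR or PR (15.3.3) | CR, CRi or PR (5.6.2.1) |
| Source of the call | Table 3 criteria; assessor not specified as masked | Site entry; derivation optional and exploratory |
| Criteria in force | Table 3 | Two version columns, no governing rule |
| PR blast fall | "decrease of pre-treatment bone marrow blast percentage by at least 50" per cent, plus blasts 5–25% | 5–25% with normal counts, as legible |
| Transfusion condition for CR | Red cells only | All transfusions, as legible |

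The first three rows do not depend on how the tables were read from PDF. The last two do: nothing appears under the V7 column of SAP Table 4 in the extracted text, so its cells may be merged or lost.

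**Weight of one patient.** With 41 control and 82 GRASPA patients (protocol 15.2), 1/41 = 2.4 points and 1/82 = 1.2 points.

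**Counting CRi or not (assumed rates).** Take CR + PR as 23% in control and 30% with GRASPA. The odds ratio is (0.30/0.70)/(0.23/0.77) = 1.43. Adding CRi:

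| CRi control / GRASPA | Odds ratio with CRi |
|---|---|
| 5% / 5% | (0.35/0.65)/(0.28/0.72) = 1.38 |
| 5% / 10% | (0.40/0.60)/(0.28/0.72) = 1.71 |
| 5% / 15% | (0.45/0.55)/(0.28/0.72) = 2.10 |
| 10% / 5% | (0.35/0.65)/(0.33/0.67) = 1.09 |

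**Over-calling in one arm (assumed).** Let the true rate be 18% in both arms, borrowing the low-dose cytarabine complete remission rate quoted in protocol 3.1. Let a fraction f of GRASPA non-responders be called responders. The apparent GRASPA rate is 0.18 + 0.82f. The last column is the exact binomial probability, with 41 and 82 patients, that a pooled two-proportion z test at two-sided 0.05 favours GRASPA. It is an unadjusted stand-in for the planned logistic regression.

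| f | Apparent rate | Odds ratio | Chance of a nominally significant benefit |
|---|---|---|---|
| 0% | 18.0% | 1.00 | 2.1% |
| 5% | 22.1% | 1.29 | 6.8% |
| 10% | 26.2% | 1.62 | 16.3% |
| 15% | 30.3% | 1.98 | 30.9% |

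**PR rule, conditional on Table 4.** The blast ceiling under protocol Table 3 is min(25%, baseline/2). Under the legible SAP text it is 25%. The two differ only for baseline blasts below 50%. At a baseline of 30% the ceilings are 15% and 25%, and a move from 30% to 25% is a relative fall of 5/30 = 16.7%. Both texts also require the haematologic criteria of CR, which limits how many patients could be affected. These figures apply only if the legible text really is the SAP's V7 definition.

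**The case against.** The strongest reply has four parts.

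1. *The SAP does define one composite.* This stands. CR, CRi or PR is fixed in a document to be signed before database lock, and the components are reported separately. Protocol 4.3.2 also lists CR, CRi and PR together as the response endpoint. A reader might infer that the composite could be picked after the data are seen; the documents do not support that. What remains is an undeclared conflict with protocol 15.3.3.

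2. *The PR and transfusion differences may be a PDF artefact.* This also stands. The legible Table 4 text includes categories absent from protocol V7 Table 3, such as cytogenetic and molecular CR, so it may be the older definition. A reader might infer that the SAP drops the 50% blast fall from the current definition. That cannot be asserted with the V7 column empty.

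3. *The SAP's remark on criteria may simply mean the several components of response.* This is possible. That it refers to the V7 re-definition is inference, not something the SAP states. The missing governing rule does not depend on it, because Table 4 itself sets out two versions.

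4. *CR rests largely on counts, and investigators can use judgement a program cannot.* Partly right. The notes to protocol Table 3 allow repeat marrows and flow cytometry for ambiguous cases, and Table 3 gives no time window for transfusion independence. A derivation therefore needs further specification. This argues for keeping site calls as a sensitivity analysis, not for making them the main one.

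**Conclusion.** The point holds as an inexpensive improvement to a secondary endpoint. Three facts are firm. The main analysis uses site-entered calls in an open-label trial with no described masked review. No rule says which protocol version's criteria govern the pooled regression. The composite differs between protocol and SAP without being declared in SAP section 6.

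The documents do not show that any bias exists, or in which direction. The odds ratios above are illustrations under assumed rates. A reader might infer that the go/no-go decision is compromised. The documents do not support that: protocol 15.3.1 and SAP 5.1 base the judgement of promise on the OS hazard ratio, which response calls cannot change. Response enters only through the wider weighing of endpoints in the SAP Introduction. The PR and transfusion wording is a matter to check, not an established error.

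**What to change.** Before database lock, amend the SAP as follows.

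- Make the main objective-response analysis a programmed best response from recorded data, applying protocol V7 Table 3 identically to every ITT patient whichever version was in force at the visit.
- Specify how missing components and ambiguous marrows are handled, and set the window for transfusion independence. Define CRp or remove it.
- Keep site-entered response as a sensitivity analysis, with a table of discordant cases by arm.
- Keep the composite CR + CRi + PR and the separate component percentages already planned. Declare the difference from protocol 15.3.3 in SAP section 6.
- Check SAP Table 4 against protocol Table 3. Correct the PR and transfusion wording only if the V7 column really carries the text shown.
- Either describe the central reading named in listing 16.2.6.2 or correct the title.

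The cost is SAP text, one derivation program and its specification. Disease assessment at each course, blood counts and transfusions are already scheduled for collection (protocol 8.6 to 8.8), though some components may be missing at some visits. Patients lacking a component count as non-responders, in line with the SAP's existing denominator rule, so rates may be slightly lower.
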